#### **Methodology:**

This is a clinical trial that will enroll approximately 100 subjects from three different research sites. Patients who have been diagnosed with cyclic vomiting syndrome and enrolled in our study will be given standard treatment of 2.5mg droperidol IV, 8mg ondansetron IV or 5mg haloperidol IM per physician's choice. The research specialist will be notified when the drugs are administered and view the patient's chart to determine if the reason for the anti-nausea drug was a diagnosis of cyclic vomiting syndrome. If so, the patient's nurse will be messaged via EPIC to inquire on the patient's pain and nausea scores initially versus two hours after the drug is administered, if at the St. Joseph ED, research specialist will make contact with the patient and ask pain/nausea scores at baseline and 2 hours later themselves.

Inclusion criteria will be adult patients with a clinical diagnosis of cyclic vomiting in the ED

Exclusion criteria would include pregnancy, allergy to any of the study medicines

Primary outcome will be change in pain and nausea at 2 hrs using a visual analog scale of 0-10

Secondary outcome will be:

1. Change in pain [ Time Frame: 1, 2, 24 and 48 hours ]

Changes in abdominal pain score at 1, 2, 24 and 48 hours vs. baseline

2. Change in nausea [ Time Frame: 1, 2, 24 and 48 hours ]

Changes in nausea score at 1, 2, 24 and 48 hours vs. baseline

3. Treatment success [ Time Frame: 2, 24 and 48 hours ]

Treatment success = both abdominal pain and nausea score < 2 at 2, 24 and 48 hours

4. Discharge ready at 2 hours [ Time Frame: 2 hours ]

Deemed discharge-ready at 2 hours in the opinion of the treating physician

5. Rescue anti-emetics in ED [ Time Frame: at discharge from Emergency Department or 12 hours whichever comes first ]

Given rescue anti-emetics prior to discharge

6. Time to discharge from ED [ Time Frame: at discharge from Emergency Department or 12 hours whichever comes first ]

Time interval to discharge-ready from t=0 (min)

Subject preferred Time to Discharge from ED" > 12 hours (binary yes/no)

7. Return to ED [ Time Frame: 7 days ]

Unscheduled return visits to ED within 7 days (count)

8. Prolonged ED Length of stay [ Time Frame: at discharge from Emergency Department or 12 hours whichever comes first ]

Outcome 10 "

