**Research Design:**

Patients presenting with a chief complaint of vomiting and abdominal pain will be screened by the bedside provider for the diagnosis of cyclic vomiting or cannabis induced vomiting syndrome. Per the doctor's choice, 2.5mg droperidol, 5mg haloperidol or 8mg odansteron will be administered. The remaining portion of the patients care is at the discretion of the treating provider including the use of fluids, laboratory diagnostics and radiographic diagnosis and pain medications. The research specialist will be notified when the drugs are administered and view the patient's chart to determine if the reason for the anti-nausea drug was a diagnosis of cyclic vomiting syndrome. If so, the patient's nurse will be messaged via EPIC to inquire on the patient's pain and nausea scores initially versus two hours after the drug is administered, if at the St. Joseph ED, research specialist will make contact with the patient and ask pain/nausea scores at baseline and 2 hours later themselves. Our research specialist will contact patients 1 and 2 days following treatment and enter responses into the project spreadsheet housed on Spectrum Health Lakeland servers. The provider may, at any time choose to add additional anti emetics at their choice but this will be considered as a "rescue" medication for the purposes of this study. All enrolled patients will be added to a study list where the medication given as well as the the secondary outcomes will be recorded on a secure spreadsheet for analysis later.

Continuous variables (such as pain and nausea score, length of stay in the ED will be analyzed using 2 tailed student t-tests. Qualitative variables (number with 2 point improvement in abd pain and nausea score, discharge state at 2 hours, need for rescue anti-emetic, return to ED) will be analyzed using chi-squared analysis.

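### Pain is a primary score, but the plan does not say how analgesics are recorded or handled, so an imbalance in their use could bias the 2-hour pain comparison

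*Combined protocol and SAP*

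**What the plan says.** Methodology sets the primary endpoint: "Primary outcome will be change in pain and nausea at 2 hrs using a visual analog scale of 0-10". It gives no weights and no ranking of the two scores. Pain enters again in secondary outcome 3: "Treatment success = both abdominal pain and nausea score < 2 at 2, 24 and 48 hours".

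Research Design covers treatment and data:

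- Allocation is not random: "Per the doctor's choice, 2.5mg droperidol, 5mg haloperidol or 8mg odansteron will be administered".
- Other care is left to the provider, "including the use of fluids, laboratory diagnostics and radiographic diagnosis and pain medications", with no condition on timing.
- The provider may "choose to add additional anti emetics at their choice but this will be considered as a" rescue medication. Secondary outcome 5 matches this: "Given rescue anti-emetics prior to discharge". Analgesics appear in neither place.
- For each patient, "the medication given as well as the the secondary outcomes will be recorded on a secure spreadsheet". In context the medication is the study drug, and no secondary outcome is analgesic use.

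The planned analyses are two-tailed t-tests (Research Design) and ANOVAs of baseline and 2-hour scores for the three drugs (Statistical Analyses). Neither section names a covariate, a rule for analgesia given before the 2-hour score, or a sensitivity analysis.

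**The concern.** The nausea score has a marker for additional treatment, because an added anti-emetic is counted as rescue. The pain score has none. A patient given an analgesic before, with or after the study drug contributes an ordinary 2-hour pain score and can still be a treatment success.

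Under randomisation, analgesia before the study drug would balance in expectation. Here the clinician who picks the study drug may also pick the analgesic, at three sites. Ethical Considerations adds that droperidol had not been in common use in these departments, so drug choice may follow prescriber habit. Analgesic habits could differ along the same line, and balance cannot be assumed.

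Two results are exposed. The between-drug comparison of 2-hour pain absorbs any imbalance that is unrelated to drug effect. The change from baseline within each drug includes analgesic relief even when use is balanced. That matters because the ANOVA is described in terms of baseline against 2 hours.

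**Working it through.** The plan gives no figure to reproduce: the target of about 100 patients comes with no alpha, power, effect size or standard deviation. What follows is an illustration.

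**From the documents:** about 100 patients; three drugs; a 0-10 scale; and the cited haloperidol-ondansetron difference of 2.3 cm (Theoretical Framework), used only for scale.

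**Assumed, not in the documents:** equal groups, n = 100/3 ≈ 33 per drug; two-sided alpha 0.05; SD of pain change 2.5 to 3.5; mean analgesic effect e on 2-hour pain of 1 to 3 points; difference in analgesic use between two drugs, d, of 0 to 40 percentage points, unrelated to drug effect.

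**Step 1. Spurious between-drug difference,** b = d × e, in points:

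| d | e = 1 | e = 2 | e = 3 |
|---|---|---|---|
| 0 | 0 | 0 | 0 |
| 0.20 | 0.2 | 0.4 | 0.6 |
| 0.30 | 0.3 | 0.6 | 0.9 |
| 0.40 | 0.4 | 0.8 | 1.2 |

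Only the difference in use matters: 20% v 40% and 30% v 50% both give 0.20 × 2 = 0.4. Against 2.3 cm, the non-zero values run from 0.2/2.3 = 9% to 1.2/2.3 = 52%.

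**Step 2. False-positive rate of one pairwise test with no true drug difference,** by normal approximation:

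se = SD × √(2/n); rate = Φ(b/se − 1.96) + Φ(−b/se − 1.96).

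- At SD 3, se = 3 × √(2/33.3) = 0.735.
- b = 0: 5%.
- b = 0.4: b/se = 0.544; Φ(−1.416) + Φ(−2.504) ≈ 8.5%.
- b = 0.6: b/se = 0.816; Φ(−1.144) + Φ(−2.776) ≈ 13%.
- Smallest non-zero case (b = 0.2, SD 3.5): about 6%.
- Extreme corner (b = 1.2, SD 2.5): about 50%. This needs both a 40-point imbalance and a 3-point effect.

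**Step 3. Within-drug change.** Inflation = share given an analgesic × e. At 50% use and 2 points it is 0.5 × 2 = 1.0 point. From 25% use with 1 point to 75% use with 3 points, it runs from 0.25 to 2.25. This does not depend on imbalance. It applies to analgesic effect that falls between the baseline and 2-hour scores; relief already present at baseline is in the baseline score.

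**The case against.** **The data exist.** A reader might infer that analgesic use is unrecorded and therefore cannot be examined. The documents do not support that. They show only that no analgesic field is named for the spreadsheet, which is an inference from silence. The research specialist already views each patient's chart, so the information is probably recoverable, and the fix relies on this.

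**Bias is conditional.** A reader might also infer that the drug comparison is biased. It is biased only if analgesic use differs by drug for reasons other than drug effect; with equal use the between-drug bias is zero. If more analgesic follows one drug because that drug works less well, the observed 2-hour score is a legitimate result for that drug under usual care. The provider-discretion design, and the stated interest in the relative utility of the medicines, fit such a treatment-policy reading. This stands, and it is why the as-observed score should remain the main result. But the plan does not state that reading, and it does not cover analgesia given before the study drug, which cannot be a consequence of it.

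**A composite imports prescribing habits.** Counting a patient given an analgesic as a non-success moves any difference in prescribing straight into the success rate. Treatment success is also not named in either analysis paragraph. Both points stand, so such an analysis can only be supportive.

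**It is one confounder among several.** Fluids are in the same sentence, and physician choice with unadjusted tests is the larger problem. This is true. Analgesia merits its own line because it acts directly on a primary score.

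**Conclusion.** The point holds in conditional form. Followed as written, the plan leaves a plausible confounder of a primary score unexamined and does not say what the 2-hour pain score represents when an analgesic has been given.

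The direction and actual size are unknown. Under the assumed inputs the spurious between-drug difference is 0 to 1.2 points. A middle case (30-point imbalance, 2-point effect, SD 3) gives 0.6 points and raises one pairwise false-positive rate from 5% to about 13%. All of this rests on assumed effects, usage differences, SDs and equal groups.

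This is a modest improvement to the analysis. It deals with one part of the confounding by physician choice, and nothing in it calls for a change to how pain is treated.

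**What to change.** Leave care unchanged and make these changes to data and analysis:

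1. Extract from the patient chart the name and time of each analgesic given up to the 2-hour score.
2. In the 2-hour pain analysis, add two covariates to drug: baseline pain, and analgesia at or before study-drug administration (yes/no). Analgesics given together with the study drug fall in this category. Do not adjust for analgesia given afterwards.
3. Report, by drug, the percentage given an analgesic after dosing and up to 2 hours.
4. Keep the as-observed 2-hour score as the main result and describe it as the effect of study drug plus usual care.
5. Optionally, add a 2-hour success analysis in which an analgesic or rescue anti-emetic between dosing and 2 hours counts as non-success. Label it supportive and note that it also reflects prescribing habits.

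If the times cannot be extracted, state that the 2-hour pain change reflects study drug plus uncontrolled analgesia.

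The cost is chart extraction for about 100 patients at three sites, two covariates and one descriptive table. Success rates in the optional analysis can only be equal or lower. Statistical Analyses is written in the past tense, so if data collection is complete the added analyses should be labelled post hoc.

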**Title:** A comparison of haloperidol 5mg IM vs droperidol 2.5mg and ondansetron for the treatment of hyperemesis in cyclic vomiting syndrome

**NCT#:** NCT05065567

**Date:** 5/19/2025

**Introduction or Background:** Over the past 5 years there has been a 609% increase in persistent vomiting (cyclic vomiting syndrome) related hospitalizations. Many of these have been associated with cannabis use. Despite this significant increase in frequency there is scant literature on the most effective treatment of this condition. A variety of acceptable treatments include ondansetron (Zofran), haloperidol (Haldol) and droperidol. A recent study by Ruberto et al found haloperidol superior to ondansetron for treatment of this condition. Droperidol, a similar D2 agent like haloperidol has been widely used as another treatment option for cyclic vomiting. To date, the two agents have not been compared to determine superiority in managing the symptoms related to cyclic vomiting.

**Problem and Purpose Statement-** The purpose of this study is to compare two commonly used agents for the treatment of cyclic vomiting to see if one agent is inferior to the other in time to improvement in symptoms, need for repeat or rescue medications, treatment failures and complications/side effects. To date, no head to head studies have been published with these two agents.

**Research Questions or Hypothesis:** Is droperidol or haloperidol inferior to the other agent in reducing symptoms related to cyclic vomiting.

**Theoretical Framework-Present Knowledge:** In a recent head to head study, Ruberto et al found that Haloperidol was superior to ondansetron (difference 2.3 cm [95% confidence interval 0.6 to 4.0 cm]; P=.01), with similar improvements in both pain and nausea, as well as less use of rescue antiemetics (31% versus 59%; difference -28% [95% confidence interval -61% to 13%]) and shorter time to emergency department (ED) departure (3.1 hours [SD 1.7] versus 5.6 hours [SD 4.5]; difference 2.5 hours [95% confidence interval 0.1 to 5.0 hours]; P=.03). Haldol, a D2 receptor antagonist, is thought to help suppress the nausea centers of the brain and reduce symptoms from cyclic vomiting. Droperidol, also a D2 antagonist is theorized to have a similar effect. Droperidol has been noted to possibly have a faster time of onset than haloperidol and droperidol is routinely used IV while haloperidol is typically a IM injection.

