#### **Informed consent**

Patients experiencing cyclical vomiting exacerbations tend to be very symptomatic and are very uncomfortable. The HAVOC trial (Ruberto et al) experienced low enrollment due to patients not being able to participate in consent discussions. The medicines we are proposing to use are all medicines that have been effective for cyclic vomiting, but it is unknown if droperidol, a relatively recent re-addition to clinicians' pharmacologic armamentarium is better or worse than haloperidol. We feel that since clinicians are going to try droperidol for these patients anyway, we would like to formally assess its utility. We do not want to delay these patients' treatment to go over a lengthy consent document for medicines that will frequently be used in any case, and these patients will often not tolerate carrying this discussion out

**Statistical Analyses:** Means and standard deviations were reported for baseline pain and nausea and for pain and nausea after 2 hours of drug administration for the three arms of the study. ANOVAs were conducted to determine whether significant differences existed between baseline and 2 hours after drug administration for the three drugs. Due to low response rate at 24 and 48 hours (6 pts), these time points were not included in the analysis.

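### The study question is droperidol versus haloperidol, but neither the planned t-tests nor the reported three-drug ANOVA is tied to that contrast, and no rule covers the other two drug pairs

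*Combined protocol and SAP*

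**What the plan says.** - **Question.** Research Questions or Hypothesis asks: "Is droperidol or haloperidol inferior to the other agent in reducing symptoms related to cyclic vomiting". That is one contrast.
- **Groups.** Methodology lists three treatments, "2.5mg droperidol IV, 8mg ondansetron IV or 5mg haloperidol IM", chosen by the physician. Research Design repeats the three drugs.
- **Primary outcome.** Methodology: "Primary outcome will be change in pain and nausea at 2 hrs using a visual analog scale of 0-10".
- **Planned tests.** Research Design: "Continuous variables (such as pain and nausea score, length of stay in the ED will be analyzed using 2 tailed student t-tests". Categorical outcomes "will be analyzed using chi-squared analysis". Neither sentence says which drugs are compared with which.
- **Reported tests.** The Statistical Analyses paragraph, placed under Informed consent, says "ANOVAs were conducted to determine whether significant differences existed between baseline and 2 hours after drug administration for the three drugs". It covers pain and nausea at baseline and 2 hours, does not mention ED length of stay, and names no follow-up pairwise comparison.
- **Not stated anywhere.** A significance level, the order of comparisons, or an adjustment for several comparisons.

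**The concern.** A t-test compares two groups and the study has three, so the Research Design sentence can mean one comparison or as many as three. If three are run without adjustment, any one of them can be reported as a drug difference, although only one answers the question asked.

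The ANOVA does not close the gap. An overall three-group test says that some drug differs, not which one. The background already cites haloperidol as better than ondansetron by 2.3 cm. An overall result driven by ondansetron is therefore a realistic prospect, and a reader could take it for a difference between droperidol and haloperidol.

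At stake is whether the study gives an error-controlled answer to its own question.

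**Working it through.** **Inputs.** Three drugs and about 100 subjects (Methodology). Two-tailed t-tests (Research Design). Difference of 2.3 between haloperidol and ondansetron (Theoretical Framework), taken here as 2.3 points on the 0-10 scale. Assumptions: 5% two-sided per test; SD of the 2-hour change of 2, 3 or 4 points; group sizes as shown, since allocation is by physician's choice. The documents give no alpha, power or sample-size figure, so there is none to reproduce.

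**1. Three unadjusted t-tests, no true difference.**
- With equal groups, at least one pair is significant when the range of the three means, in standard errors of a mean, exceeds 1.96 × √2 = 2.77. The studentized range for three groups gives 12.2% in large samples and 12.1% on 97 degrees of freedom (using the t critical value).
- Simulated at or near 100 subjects, from equal thirds to 80/10/10, the result is 11.6% to 12.2%.
- For reference, independent tests would give 1 − 0.95³ = 14.3%, and the upper bound is 3 × 5% = 15%.
- The overall F-test gives 5.0%. Pairwise t-tests run only after a significant F give 4.9% to 5.0%.
- Droperidol versus haloperidol alone gives 5%.

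**2. Overall F-test when only ondansetron differs.** Let droperidol equal haloperidol, with ondansetron worse by 2.3 points. With n_o subjects on ondansetron out of N, the noncentrality is λ = 2.3² × n_o(N − n_o)/N ÷ SD².
- At 33/33/33: n_o(N − n_o)/N = 33 × 66/99 = 22, and 5.29 × 22 = 116.38.
- At 45/45/10, with 10 on ondansetron: 10 × 90/100 = 9, and 5.29 × 9 = 47.61.

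| Split | SD 2 | SD 3 | SD 4 |
|---|---|---|---|
| 33/33/33: λ | 29.1 | 12.9 | 7.3 |
| 33/33/33: F significant | 99.9% | 90% | 66% |
| 45/45/10: λ | 11.9 | 5.3 | 3.0 |
| 45/45/10: F significant | 87% | 51% | 31% |

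The percentages come from the noncentral F distribution with critical value 3.09; simulation agrees within about a point. In the same scenario the droperidol-haloperidol t-test is significant in only about 5% of studies.

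**3. What a repair achieves, no true difference.**
- Droperidol-haloperidol at 5%, plus a separate Holm-adjusted 5% for the two ondansetron pairs: 8.0% to 8.6% for any false pair.
- The same, with the ondansetron pairs tested only after a significant primary contrast: about 5%, because no false pair can be declared unless the primary test is itself falsely significant.

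**The case against.** **The question is one pair, so a t-test is the natural tool and the error is 5%.** This is fair as a reading. The documents never say that all three pairs will be tested. Nor do they limit testing to one: Research Design names no pair, and Statistical Analyses reports all three arms.

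**The ANOVA already controls the error.** If it were a between-drug test and a stated gate, it would hold the rate near 5%. No gate is written. The wording, between baseline and 2 hours, leaves open whether it tests change within a drug or differences between drugs. It also leaves ED length of stay on t-tests.

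**The figures in step 2 are not error rates.** Correct. They are power to detect a real ondansetron difference, and harm arises only if someone misreads the overall result. They show that such a result says little about the stated pair. They also fall with few ondansetron subjects.

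**A stronger reading is tempting:** that the chance of a false drug difference is 12% on any outcome. The documents do not support it. The 12% needs three pairs t-tested at an unstated 5%. For pain and nausea it also needs Research Design to prevail over Statistical Analyses. Categorical outcomes may each get one three-group chi-squared test at 5%.

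**Physician's choice of drug can itself create group differences.** This stands. No multiplicity rule addresses it, and neither 5% nor 12% is the study's actual rate of misleading differences.

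**Conclusion.** The concern holds in conditional form. Neither stated test, as written, gives a controlled answer to the droperidol-haloperidol question.

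- **If three t-tests are run:** about 12% chance of a false difference per continuous outcome so tested. That means ED length of stay, and pain and nausea if Research Design governs. This assumes 5% per test and groups that differ only by chance.
- **If the ANOVA governs as a between-drug test:** its own error is about 5%, but ondansetron alone could make it significant in 31% to 99.9% of studies over the splits and SDs tried, with droperidol and haloperidol equal.

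A reader might infer that the reported analysis carries a 12% error, or that its authors read the ANOVA as a droperidol-haloperidol result. The documents show neither. What they show is two different tests for the same scores and no named contrast. This is worth correcting because it governs how any result may be interpreted.

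**What to change.** Reconcile Research Design and Statistical Analyses so that both state the following:

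1. Droperidol versus haloperidol is the single primary contrast, tested at two-sided 5% and reported with a 95% confidence interval.
2. The two ondansetron comparisons are secondary. They are tested only if the primary contrast is significant, and then Holm-adjusted. Otherwise they are reported as estimates with 95% confidence intervals.
3. The same order applies to the chi-squared outcomes.
4. A significant overall three-drug test is not evidence of a droperidol-haloperidol difference.

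The condition in item 2 matters: it keeps the chance of any false pair at about 5% when the drugs do not differ, against about 8% if the ondansetron pairs get a separate 5%.

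**Cost.** A few sentences and no new data. The ondansetron comparisons lose standing and face a stricter threshold (2.5% for the smaller p value). Statistical Analyses is written in the past tense, so the order must be labelled post hoc and cannot be presented as prespecified. The change does nothing about confounding from physician's choice of drug.

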#### **Ethical Considerations:**

Risks (current and potential).: As all three are standard care the risks are limited to the usual risks associated with treating this condition to include standard medicine reactions, somnolence and dystonic reaction (known with D2 antagonists) and possible QT prolongation (known in all 3 medications). Patients will receive standard care for any side effects of medicine as per standard practice of Emergency Medicine.

**Potential benefits** to the group or class from which the subjects are recruited. Potential benefits to society.

Droperidol has not been commonly used in our emergency departments in the past and if this medicine works better than the others then these patients could experience decreased length of stay and improved time to improvement of symptoms. It is our hope that this project could help guide treatment for this group of patients in the future.

The risk/benefit ratio remains the same whether patients are participating in this study or not. Our clinicians would be using these medicines to treat cyclic vomiting. By formally evaluating response we hope to provide better feedback to physicians going forward with regard to the relative utility of these medicines

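### ED length of stay is assigned an equal-variance t-test although the only ED-time SDs cited are unequal and group sizes are left to physician choice; naming Welch's test is a small, inexpensive correction

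*Combined protocol and SAP*

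**What the plan says.** The last paragraph of Research Design sets one rule for all continuous outcomes and names ED length of stay among them: "Continuous variables (such as pain and nausea score, length of stay in the ED will be analyzed using 2 tailed student t-tests". No unequal-variance version, variance check, transformation or rank alternative appears. The later Statistical Analyses paragraph describes ANOVAs after summarising pain and nausea only, so it does not replace the rule for ED time.

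The section on present knowledge cites an earlier randomised trial of haloperidol against ondansetron, with time to ED departure of "3.1 hours [SD 1.7] versus 5.6 hours [SD 4.5]; difference 2.5 hours". These are two of the three drugs studied here.

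Allocation is not controlled: "Per the doctor's choice, 2.5mg droperidol, 5mg haloperidol or 8mg odansteron will be administered". The planned total is about 100 patients, with no allocation ratio or target per drug. Ethical Considerations adds: "Droperidol has not been commonly used in our emergency departments in the past".

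**The concern.** The pooled test estimates one common variance. With equal groups it tolerates unequal spreads well. With unequal groups it does not: if the more variable drug has fewer patients, the standard error is too small and false positives rise; if it has more patients, the standard error is too large and real differences are missed. Here the size and direction of any imbalance depend on how often clinicians prescribe each drug, which has nothing to do with efficacy. Shorter stay is one of the benefits the document hopes to show, so a distorted test of it could mislead readers either way.

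**Working it through.** **Inputs from the document.** Haloperidol: mean 3.1 h, SD 1.7 h. Ondansetron: mean 5.6 h, SD 4.5 h. Total about 100 over three drugs. The plan states no alpha, power or sample-size calculation, so it has no figure to reproduce. The cited difference checks: 5.6 − 3.1 = 2.5 h.

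**Assumptions.** Two-sided nominal 5%. Group splits are not given, so a range is shown, always as low-SD group : high-SD group.

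**SD ratio, two readings.**
- Cited SDs hold under equal means: 4.5 / 1.7 = 2.65 (variance ratio 7.0).
- Only the coefficients of variation hold under equal means: 1.7 / 3.1 = 0.548 and 4.5 / 5.6 = 0.804, so the SD ratio is 0.804 / 0.548, about 1.465.

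**Formula.** In large samples the actual error of the pooled test is 2 × [1 − Φ(1.96 × SE_pooled / SE_true)], where
- SE_pooled² = {[(n1 − 1)s1² + (n2 − 1)s2²] / (n1 + n2 − 2)} × (1/n1 + 1/n2)
- SE_true² = s1²/n1 + s2²/n2

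**Ratio 2.65, split 60:20.** Pooled variance = (59 × 2.89 + 19 × 20.25) / 78 = 7.119. SE_pooled = √(7.119 × 0.0667) = 0.689. SE_true = √(2.89/60 + 20.25/20) = 1.030. Quotient 0.669; 1.96 × 0.669 = 1.31; error 19%.

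**Ratio 2.65, split 20:60.** Pooled variance = (19 × 2.89 + 59 × 20.25) / 78 = 16.02. SE_pooled = 1.033, SE_true = 0.694, quotient 1.489; 1.96 × 1.489 = 2.92; error 0.35% (0.4% by simulation).

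**Ratio 1.465, same splits (s1 = 1, s2 = 1.465).** At 60:20 the pooled variance is (59 + 19 × 2.146) / 78 = 1.279, SE_pooled = 0.292, SE_true = 0.352, quotient 0.829, error 10%. At 20:60 the quotient is 0.353 / 0.293 = 1.205, error 1.8%.

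**Simulation, normal data, equal means:**

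| Split | Pooled, ratio 2.65 | Pooled, ratio 1.465 | Welch, ratio 2.65 |
|---|---|---|---|
| 33:33 | 5% | 5% | 5% |
| 40:30 | 8% | 6% | 5% |
| 45:20 | 15% | 9% | 5% |
| 60:20 | 19% | 10% | 5% |
| 20:45 | 0.9% | 2.5% | 5% |
| 20:60 | 0.4% | 2% | 5% |

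With equal SDs the pooled error was about 5% in every split tried.

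**Skewed (gamma) data at ratio 2.65.** The pooled test gives about 9%, 16% and 20% at 40:30, 45:20 and 60:20. Welch gives about 5% to 8% over the tabled splits, and about 9.5% at the more extreme 55:11. Even at 33:33 both tests sit at 6% to 7%; that excess comes from skewness and not from pooling.

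**Power.** At 20:45, with the cited means and SDs and gamma data, power is 76% for the pooled test and 92% for Welch.

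**The case against.** The strongest objection is that the large figures combine SDs observed at unequal means with a null of equal means. Times cannot be negative, and here the larger SD goes with the larger mean, so under a true null the SDs may well be closer. This stands, and it is why the ratio of 1.465 is shown beside 2.65.

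Second, the cited figure is time to departure in a randomised trial of intravenous haloperidol. This study gives haloperidol IM and measures time to discharge-ready in a window that ends at 12 h. If values stop at 12 h (one reading of the outcome table), a gamma distribution with mean 5.6 and SD 4.5 keeps an SD of about 3.5, and the ratio falls to about 3.5 / 1.7 = 2.1. This also stands as a reason to treat 2.65 as close to the upper end.

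Third, no split is documented. Physician choice and the limited past use of droperidol make imbalance plausible, but they fix neither its size nor its direction, and at 40:30 the error is only 6% to 8%.

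Fourth, a reader might infer that the headline droperidol-haloperidol comparison, or the primary pain and nausea analysis, is shown to have a wrong error rate. The documents do not support that. They give no droperidol SD and no SD for either score, and the Statistical Analyses paragraph describes ANOVAs for the scores.

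Finally, Welch is a partial remedy for skewed times, and neither test corrects for non-random drug choice. Both statements are true. They limit the importance of the point, but the plan still names a test whose assumption its own cited figures call into question.

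**Conclusion.** The point holds as a minor one about a secondary outcome. For haloperidol versus ondansetron on ED time, the planned test's actual error at a nominal 5% lies between about 0.4% and 19% if the cited SDs carry over to the null, and between about 2% and 10% if only the coefficients of variation do. It is about 5% if groups or SDs are equal. These ranges rest on an assumed two-sided 5% level, assumed splits from 60:20 to 20:60, normal data, and Student's t-test meaning the pooled version. If Welch was intended, adding its name settles the matter.

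It would be too strong to say that this trial's false-positive rate is 19%: that figure needs both the full 2.65 ratio and a 3:1 split with the variable drug in the smaller group. The size of any effect on the droperidol-haloperidol contrast is unknown.

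**What to change.** In the analysis paragraph of Research Design, specify two-sided Welch (unequal-variance) t-tests for pairwise ED-time comparisons and Welch's ANOVA for any test across the three drugs, and report the number of patients per drug beside each result. Using Welch for the pain and nausea scores is an optional precaution, since the document gives no SDs for them.

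The cost is one line of wording and no new data. Almost no power is lost if the SDs turn out equal. Welch remains slightly anti-conservative, about 5% to 8% in the gamma simulations above, when times are skewed and the smaller group has the larger SD. Confounding by drug choice is the larger problem and needs its own remedy.
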